9.4.3 Handling of missing values/censoring/discontinuations

All missing data, which are missing due to an assessment not having been made, will be treated as "missing at random". Patients with partial data will be included in the primary analysis. Where a missing data value occurs, this will be set to missing in the analysis. For the combined baseline of screening and baseline data, where only screening or baseline data is available, this value will be taken as the baseline. If no pre-treatment data is available, the subject will be excluded from the analysis when comparing the change to pre-treatment values.

Pure tone audiometry values which are missing because the hearing threshold exceeded the upper limit of the machine will be imputed with the value of 5dB above the upper limit of the machine.

9.4.4 Supportive analyses

Not applicable.

9.5

 Commercially Confidential

 Analysis of secondary
 Information
 variables

Secondary variables will be analyzed descriptively.

9.5.1 Efficacy

Secondary efficacy variables will be reported descriptively.

9.5.2 Safety

Vital signs

All vital signs data will be listed by treatment, patient, and visit/time and if ranges are available abnormalities (and relevant orthostatic changes) will be flagged. Summary statistics will be provided by treatment and visit/time.

ECG evaluations

All ECG data will be listed by treatment, patient and visit/time, abnormalities will be flagged. Summary statistics will be provided by treatment and visit/time.

Clinical laboratory evaluations

All laboratory data will be listed by treatment, patient, and visit/time and if normal ranges are available abnormalities will be flagged. Summary statistics will be provided by treatment and visit/time.

Adverse events

All information obtained on adverse events will be displayed by treatment and patient.

The number and percentage of patients with adverse events will be tabulated by body system and preferred term with a breakdown by treatment. A patient with multiple adverse events within a body system is only counted once towards the total of this body system. Exact 95% binomial confidence intervals may be provided for AE rates. If a dose-related safety signal is suspected, this may be confirmed by a permutation contrast test t using the nominal dose level as contrast.

Confidential

Other safety evaluations

Not applicable.

Commercially Confidential Information

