Eligible patients will return to the study center at baseline (Day -3 to -1) and undergo pre-operative preparation as well as pre-treatment functional assessments.

Day 1 visit

On Day 1, study patients will undergo the required protocol assessments and the stapedotomy for delivery of the study drug to the scala vestibuli perilymphatic space of the inner ear. At the completion of the surgery and study drug infusion, study patients will recover in the surgical center's post-op facility and undergo post-surgery evaluations and assessments. Study patients may be transitioned to either the inpatient unit of the surgical center or pre-arranged temporary housing close to the surgical center.

Day 2 to Day 6 visits

Study patients will be followed up for the next 5 post surgery days (Day 2 to Day 6) and will undergo the protocol-required safety follow up evaluations. Study patients will be discharged home if there are no significant adverse events requiring prolonged monitoring. Patients will have the option to remain in the provided housing until the completion of the Day 14 visit.

Subsequent visits will be scheduled with the study patients prior to being discharged.

Day 15 visit

Study patients will return to the study center to have surgical packing removed from their ear and will also undergo study required assessments. Patients will be discharged home or to their local housing at the end of all study required evaluations. Patients will be reminded of their next scheduled visit.

Follow up and end of study visits

Total follow-up period in the trial will be 6 months after administration of CGF166. The follow-up visits will be at 2, 4, and 6 months/EOS.

Patient who have already completed Day 169 assessment ($\sim 6 \text{ month}$) will return to site to complete end of study visit (visit 777) as soon as practically possible. Patients who have not completed Day 169 will complete end of study visit (visit 777) on Day 169.

During each visit to the study center, post-operative recovery of the study ear will be monitored and evaluated. Study patients will also undergo the study-required safety, Confidential Information

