7.1 Adverse events

An adverse event (AE) is any untoward medical occurrence (i.e., any unfavorable and unintended sign [including abnormal laboratory findings], symptom or disease) in a patient or clinical investigation patient *after providing written informed consent* for participation in the study. Therefore, an AE may or may not be temporally or causally associated with the use of a medicinal (investigational) product. Pre-existing medical conditions/diseases (i.e., Medical History(ies)) are considered AEs if they worsen after providing written informed consent. Abnormal laboratory values or test results constitute AEs only if they induce clinical signs or symptoms, or are considered clinically significant, or they require therapy.

The occurrence of adverse events should be sought by non-directive questioning of the patient at each visit during the study. Adverse events also may be detected when they are volunteered by the patient during or between visits or through physical examination, laboratory test, or other assessments.

Adverse events must be recorded on the Adverse Events CRF under the signs, symptoms or diagnosis associated with them, and accompanied by the following information:

- 1. the severity grade:
 - mild: usually transient in nature and generally not interfering with normal activities
 - moderate: sufficiently discomforting to interfere with normal activities
 - severe: prevents normal activities
- 2. its relationship to study treatment
- 3. its duration (e.g., start and end date)
- 4. whether it constitutes a serious adverse event (SAE)
- 5. action taken regarding study treatment
- 6. whether other medication or therapies have been taken (concomitant medication / non-drug therapy)
- 7. its outcome

An SAE is defined as any AE which meets any one of the following criteria:

- is fatal or life-threatening
- results in persistent or significant disability/incapacity
- constitutes a congenital anomaly/birth defect
- requires inpatient hospitalization or prolongation of existing hospitalization, unless hospitalization is for:
 - routine treatment or monitoring of the studied indication, not associated with any deterioration in condition
 - elective or pre-planned treatment for a pre-existing condition that is unrelated to the indication under study and has not worsened since signing the informed consent form

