7.2 Serious adverse event reporting

Screen Failures

Note the following requirement for Screen Failures: SAEs occurring after the subject has provided informed consent until the time the subject is deemed a Screen Failure must be reported to Novartis.

Treated subjects

To ensure patient safety, every SAE, regardless of causality, occurring after the patient has provided informed consent and until 30 days after the patient has stopped study participation (defined as time of last dose of study drug taken or last visit whichever is the later) must be reported to Novartis within 24 hours of learning of its occurrence.

Any SAEs experienced after this 30 day period should only be reported to Novartis if the investigator suspects a causal relationship to the study drug.

To ensure patient safety, every SAE, regardless of causality, occurring after the patient has provided informed consent and until 30 days after the last study visit if there are post-treatment follow-up visits with no required procedures must be reported to Novartis within 24 hours of learning of its occurrence. Any SAEs experienced after the 30 day period should only be reported to Novartis if the investigator suspects a causal relationship to study treatment.

Recurrent episodes, complications, or progression of the initial SAE must be reported as follow-up to the original episode, regardless of when the event occurs. This report must be submitted within 24 hours of the investigator receiving the follow-up information. An SAE that is considered completely unrelated to a previously reported one should be reported separately as a new event.

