8.1 Safety

The second primary objective is to assess the safety and tolerability of IL CGF166.

Vital signs

All vital signs data will be listed by infusion volume, patient and visit/time and if ranges are available abnormalities (and relevant orthostatic changes) will be flagged. Summary statistics will be provided by infusion volume and visit/time.

ECG evaluations

All ECG data will be listed by infusion volume, patient and visit/time, abnormalities will be flagged. Summary statistics will be provided by infusion volume and visit/time.

Clinical laboratory evaluations

All laboratory data will be listed by infusion volume, patient, and visit/time and if normal ranges are available abnormalities will be flagged. Summary statistics will be provided by infusion volume and visit/time.

Adverse events

All information obtained on adverse events will be displayed by infusion volume and patient.

The number and percentage of patients with adverse events will be tabulated by body system and preferred term with a breakdown by infusion volume where applicable. A patient with multiple adverse events within a body system is only counted towards the total of this body system.

Magnetic Resonance Imaging (MRI)

An MRI will be used to assess the structural integrity of the inner ear at screening and following treatment. The MRI data will be listed by infusion volume, patient and visit.

Commercially Confidential Information

Columbia-Suicide Severity Rating Scale (C-SSRS)

The C-SSRS data will be listed by infusion volume, patient and visit/time.

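### Adverse event percentages are compared across infusion volumes although earlier-dosed patients can be observed past Day 169, and no common follow-up window is stated

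*Protocol*

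**What the plan says.** Protocol 3.1 states a uniform duration: "Total follow-up period in the trial will be 6 months after administration of CGF166". The same section then sets two end-of-study rules. A patient who has already completed Day 169 "will return to site to complete end of study visit (visit 777) as soon as practically possible". For the rest: "Patients who have not completed Day 169 will complete end of study visit (visit 777) on Day 169". Footnote 5 of the assessment schedule repeats both rules.

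Adverse event collection follows the visits. Protocol 7.1: "The occurrence of adverse events should be sought by non-directive questioning of the patient at each visit during the study". Serious events are reported "until 30 days after the patient has stopped study participation", which Protocol 7.2 ties to the later of last dose and last visit.

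The planned summary is a crude percentage of patients. In Protocol 9.5.2: "The number and percentage of patients with adverse events will be tabulated by body system and preferred term with a breakdown by treatment". In SAP 8.1 events are "tabulated by body system and preferred term with a breakdown by infusion volume where applicable". Protocol 9.5.2 also allows exact 95% intervals and says that, if a dose-related signal is suspected, "this may be confirmed by a permutation contrast test t using the nominal dose level as contrast". Protocol 9.4.2 makes safety and tolerability co-primary.

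Protocol 5.2 gives the volumes in dosing order: 20 µL (Cohort 1), 40 or 30 µL (Cohort 2), 40 µL (Cohort 3), 60 µL (Cohort 4), then 30 µL (Cohort 5, Part C).

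**The concern.** A crude percentage of patients with an event grows with time under observation. It compares groups fairly only if they are watched for about the same time after dosing. Here the final visit falls later for patients who had already passed Day 169, and these are the earliest dosed. Because volume was assigned in sequence, time at risk is confounded with volume.

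At stake is the only planned summary of adverse events across volumes. The permutation contrast needs patients to be exchangeable across volumes when volume has no effect. Unequal follow-up that runs with dosing order breaks that condition, so the test could respond to calendar time. The point concerns post-dose time at risk in the adverse event table. By-visit summaries of vital signs, ECG and laboratory data are not affected.

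**Working it through.** The documents give no adverse event rate and no visit 777 date, so there is no figure of the plan to reproduce. The check has three steps.

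**1. Earliest dosing calendar.** Inputs from Protocol 3.1 and the synopsis: 4 weeks between consecutive patients in Part A; in Part B, at least 4 weeks between the first patient and the other two; a review of 4-week data from the complete cohort before the next cohort. Counting from the first dose as day 0:

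- Cohort 1: 0, 28, 56
- Cohort 2: 84, 112, 112
- Cohort 3: 140, 168, 168
- Cohort 4: 196, 224, 224
- Part C: from 224 + 28 = 252

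On day 252 the Cohort 1 patients are 252, 224 and 196 days past dosing. Dosing is on Day 1, so Day 169 is 168 days after dosing. The first Cohort 2 patient is at 252 − 84 = 168 days, just reaching Day 169. On this calendar only Cohort 1 is past it.

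**2. Effect of extra time on a crude percentage.** Assume a constant hazard and a 20% risk by Day 169. Expected percentage after f days = 1 − 0.80^(f/168).

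- f = 168: 20.0%
- f = 196: 1 − 0.80^1.167 = 22.9%
- f = 224: 1 − 0.80^1.333 = 25.7%
- f = 252: 1 − 0.80^1.5 = 28.4%

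If every event occurred before Day 169, the figure would stay at 20.0% whatever the follow-up. For 252 days the range is therefore 20% (all events early) to 28% (constant hazard). With 168 extra days and constant hazard, a 10% risk becomes 1 − 0.90² = 19.0% and a 40% risk becomes 1 − 0.60² = 64.0%.

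**3. Direction across volumes with no true volume effect.** Take 20% risk by Day 169, Cohort 2 as 40, 30, 30 µL in dosing order (the split is not given), Part C at 168 days, and one calendar day for visit 777 in all patients past Day 169.

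| Assumed visit 777 day | 20 µL (n=3) | 30 µL (n=12) | 40 µL (n=4) | 60 µL (n=3) | Expected contrast |
|---|---|---|---|---|---|
| 252 | 25.7% | 20.0% | 20.0% | 20.0% | −2.49 |
| 420 | 40.6% | 22.3% | 31.0% | 23.9% | −4.86 |
| 730 | 60.6% | 26.0% | 54.3% | 49.6% | +9.05 |

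The contrast is the sum over patients of (volume − mean volume) × expected risk. The mean volume is (3×20 + 12×30 + 4×40 + 3×60)/22 = 34.5 µL. For day 252 only Cohort 1 departs from 20%, with excess 0.029 + 0.057 + 0.084 = 0.171, so the contrast is (20 − 34.5) × 0.171 = −2.49. With Cohort 2 as 40, 40, 30 µL the contrasts are −2.57, −4.16 and +10.74: the same signs.

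The day 730 row requires that no Part C patient had passed Day 169 by then, that is, that none was dosed before day 730 − 168 = 562. It shows that the sign can change and is not a forecast.

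With every patient cut at Day 169, the expected percentage under no volume effect is 20% at each volume and the expected contrast is zero.

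**The case against.** The strongest case against has four parts.

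**Size.** On the earliest calendar only three patients gain time. Their expected number with an event rises from 3 × 0.20 = 0.60 to 3 × 0.257 = 0.77, an excess of 0.17 patient. An exact 95% interval for 1 of 3 runs from about 1% to 91%, so sampling noise is far larger than the bias. Constant hazard is doubtful too: Protocol 3.6.2 describes the foreseeable risks as largely those of anesthesia and stapedotomy, and such events come early. This limits the weight of the point. It does not remove a systematic difference, and one late event moves a group of three by 33 percentage points.

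**Use.** Protocol 3.1 calls the study non-confirmatory. The intervals and the contrast are optional in Protocol 9.5.2 and absent from the visible SAP 8.1. Event dates are recorded and events are displayed by patient, so a reader of at most 22 cases can pick out late ones. That stands, but the percentages are still set out by volume with nothing to flag unequal follow-up.

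**Completeness.** Table shells and derivations sit in modules M7 and M8 (SAP 1.1), which are not available, and parts of the SAP are redacted. A window may be defined there. The visible SAP 2.2 describes four Part B cohorts and 20 to 30 Part C patients and does not mention visit 777, so it was not written around this rule.

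**Direction.** A reader might infer that lower volumes get more time, so that a true volume trend is flattened or reversed. The documents do not support that. Follow-up tracks dosing order, and 30 µL, the second-lowest volume, goes mainly to the last-dosed and largest group. The contrast can be pushed either way. A reader might also infer that Part C patients cannot be followed past Day 169. The rule depends on whether a patient has already completed Day 169, whatever the cohort, and no effective date is given.

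**Conclusion.** The concern holds in a limited form. Two end-of-study rules give unequal post-dose observation, events are collected to the final visit, and the by-volume percentages carry no common window or exposure adjustment in the visible text. Earlier-dosed cohorts, the 20 µL cohort most, can collect more events than later-dosed patients, mainly the 30 µL Part C group. The direction of any bias in the dose contrast is not fixed.

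The size is illustrative. It rests on the shortest calendar that the staggers allow, an assumed visit 777 day, a 20% risk by Day 169 and a constant hazard. The documents show neither which patients were past Day 169 nor when they returned. Nor was the Part C volume chosen from this table: Protocol 3.1 and 3.2 report that the DSMB endorsed 30 µL on preliminary data from Cohorts 1 to 4. This is a cheap improvement to the reporting of a co-primary safety objective.

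**What to change.** In Protocol 9.5.2 and SAP 8.1:

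- Keep the all-events table. In a first-in-man gene therapy study, late events should stay in the main safety display.
- Add a by-volume table restricted to events with onset from dosing to Day 169, plus the visit window.
- Base any between-volume comparison, confidence interval or dose contrast on that restricted table.
- Flag events with onset after Day 169, and show the median and range of follow-up days per volume beside both tables.

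If M7 or M8 already defines such a window, a cross-reference in SAP 8.1 is enough.

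The cost is a sentence or two of SAP text, an onset-day filter on dates already recorded (Protocol 7.1) and one extra table. The downside is that events after Day 169 do not count in the between-volume comparison.

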9.6 Sample size calculation

9.7 Power for analysis of key secondary variables

Not applicable.

9.8 Interim analyses

No interim analyses are planned in the study.

10 Ethical consideration

10.1 Regulatory and ethical compliance

This clinical study was designed and shall be implemented and reported in accordance with the ICH Harmonized Tripartite Guidelines for Good Clinical Practice, with applicable local regulations (including European Directive 2001/20/EC, US Code of Federal Regulations Title 21, and Japanese Ministry of Health, Labor, and Welfare), and with the ethical principles laid down in the Declaration of Helsinki.

10.2 Informed consent procedures

Eligible patients may only be included in the study after providing written (witnessed, where required by law or regulation), IRB/IEC-approved informed consent, or, if incapable of doing

so, after such consent has been provided by a legally acceptable representative of the patient. In cases where the patient's representative gives consent, the patient should be informed about the study to the extent possible given his/her understanding. If the patient is capable of doing so, he/she should indicate assent by personally signing and dating the written informed consent document or a separate assent form. Informed consent must be obtained before conducting any study-specific procedures (i.e., all of the procedures described in the protocol). The process of obtaining informed consent should be documented in the patient source documents.

Novartis will provide to investigators in a separate document a proposed informed consent form that complies with the ICH GCP guideline and regulatory requirements and is considered appropriate for this study. Any changes to the proposed consent form suggested by the investigator must be agreed to by Novartis before submission to the IRB/IEC, and a copy of the approved version must be provided to the Novartis monitor after IRB/IEC approval.

Women of child bearing potential should be informed that taking the study drug may involve unknown risks to the fetus if pregnancy were to occur during the study and agree that in order to participate in the study they must adhere to the contraception requirement for the duration of the study. If there is any question that the patient will not reliably comply, they should not be entered in the study.

The study includes an optional pharmacogenetic component which requires a separate signature if the patient agrees to participate. It is required as part of this protocol that the Investigator presents this option to the patient. The process for obtaining consent should be exactly the same as described above for the main informed consent.

Declining to participate in these pharmacogenetic assessments will in no way affect the patient's ability to participate in the main research study.

In the event that Novartis wants to perform testing on the samples that are not described in this protocol, additional Institutional Review Board and/or Ethics Committee approval will be obtained.

10.3 Responsibilities of the investigator and IRB/IEC

The protocol and the proposed informed consent form must be reviewed and approved by a properly constituted Institutional Review Board/Independent Ethics Committee / Research Ethics Board (IRB/IEC/REB) before study start. A signed and dated statement that the protocol and informed consent have been approved by the IRB/IEC/REB must be given to Novartis before study initiation. Prior to study start, the investigator is required to sign a protocol signature page confirming his/her agreement to conduct the study in accordance with these documents and all of the instructions and procedures found in this protocol and to give access to all relevant data and records to Novartis monitors, auditors, Novartis Clinical Quality Assurance representatives, designated agents of Novartis, IRBs/IECs/REBs, and regulatory authorities as required. If an inspection of the clinical site is requested by a regulatory authority, the investigator must inform Novartis immediately that this request has been made.

10.4 Publication of study protocol and results

Novartis assures that the key design elements of this protocol will be posted in a publicly accessible database such as clinicaltrials.gov. In addition, upon study completion and

Novartis	Confidential	Page 77
Amended Protocol Version v06 (Clean)		Protocol No. CCGF166X2201

finalization of the study report the results of this trial will be either submitted for publication and/or posted in a publicly accessible database of clinical trial results.

11 **Protocol adherence**

Investigators ascertain they will apply due diligence to avoid protocol deviations. Under no circumstances should the investigator contact Novartis or its agents, if any, monitoring the trial to request approval of a protocol deviation, as no authorized deviations are permitted. If the investigator feels a protocol deviation would improve the conduct of the study this must be considered a protocol amendment, and unless such an amendment is agreed upon by Novartis and approved by the IRB/IEC/REB it cannot be implemented. All significant protocol deviations will be recorded and reported in the CSR.

11.1 **Protocol amendments**

Any change or addition to the protocol can only be made in a written protocol amendment that must be approved by Novartis, Health Authorities where required, and the IRB/IEC/REB. Only amendments that are required for patient safety may be implemented prior to IRB/IEC/REB approval. Notwithstanding the need for approval of formal protocol amendments, the investigator is expected to take any immediate action required for the safety of any patient included in this study, even if this action represents a deviation from the protocol. In such cases, Novartis should be notified of this action and the Health Authorities (where required) and the IRB/IEC/REB at the study site should be informed within 10 working days or less, if required by local regulation.

12 References

Available upon request.

